**Table 4 Guidelines for Management of Study Treatment in Patients Who Experience Specific Adverse Events (cont.)**

Event	Action to Be Taken a
Hepatotoxicity	
Grade 2 AST or ALT elevation: (AST or ALT >3.0–5.0×ULN)	Withhold study treatment and consult with the Medical Monitor
Grade >2 AST or ALT elevation; (AST or ALT >3×ULN) in combination with total bilirubin >2×ULN or clinical jaundice as defined by Hy’s law	Discontinue study treatment and consult with the Medical Monitor. Recheck liver laboratory tests, to include AST/ALT, ALP, and total bilirubin, and CBC with differential (to determine eosinophil count), within 1 week (preferably within 72 hours). Assess patient for signs/symptoms of hepatic failure and assess for other causes of liver dysfunction (e.g. viral hepatitis, concomitant medications, etc.) Continue to monitor liver function tests until abnormalities resolve. Report Hy’s Law cases as as adverse events of special interest to the Sponsor in an expedited manner.
Grade ≥3 AST or ALT elevation: (AST or ALT >5×ULN)	Discontinue study treatment and consult with the Medical Monitor. Recheck liver laboratory tests, to include AST/ALT, ALP, and total bilirubin, and CBC with differential (to determine eosinophil count) within 1 week (preferably within 72 hours). Assess patient for signs/symptoms of hepatic failure and assess for other causes of liver dysfunction (e.g. viral hepatitis, concomitant medications, etc.) Continue to monitor liver function tests until abnormalities resolve. Elevation of AST or ALT of Grade >3 (i.e., AST or ALT >5×ULN) should be reported as an adverse event of special interest to the Sponsor in an expedited manner.
Cardiovascular Effects	
Sustained (at least two ECG measurements >30 minutes apart) QTcF that is >500 msec and/or >60 msec longer than the baseline value	Discontinue study treatment unless there is a clear alternative cause other than study drug. e
Sustained absolute QT that is >515 msec or a new ECG finding of clinical concern	Discontinue study treatment and discuss with the Medical Monitor unless there is a clear cause other than study drug. e
An episode of torsades de pointes	Discontinue study treatment.

**Table 4 Guidelines for Management of Study Treatment in Patients Who Experience Specific Adverse Events (cont.)**

Event	Action to Be Taken a
Vascular Inflammation	
Treatment emergent vasculitis	Initiate appropriate evaluation and consult with the Medical Monitor.

ALP=alkaline phosphatase; ALT=alanine aminotransferase; ANC=absolute neutrophil count; AST=aspartate aminotransferase; CBC=complete blood count; ECG=electrocardiogram; IV=intravenous; OLE=open label extension; PLT=platelet count; SLE=systemic lupus erythematosus; ULN=upper limit of normal.

Note: “Study treatment” includes study drug (GDC-0853 or placebo)

- a Patients who discontinue study drug treatment due to an adverse event should remain in the blinded study if feasible however they will not be eligible for an OLE, if initiated. If they discontinue the study, the patient should enter safety follow up.
- b Appropriate laboratory investigations, including but not limited to cultures, should be performed to establish the etiology of any serious infection.
- c Patients withdrawn from the study due to a reduced neutrophil count must be followed closely for signs of infection, with treatment and repeated laboratory analysis as deemed appropriate by the investigator including discontinuation of other treatments if indicated.
- d Patients withdrawn from the study due to a reduced platelet count should have additional management and treatment as deemed appropriate by the investigator including discontinuation of other treatments if indicated.
- e In rare circumstances, it may be acceptable to resume study drug, provided that any ECG abnormalities have resolved and that the patient is appropriately monitored. Prior to re-administering drug, consult with the Medical Monitor. Clinical judgment should be applied.

## 5.2 SAFETY PARAMETERS AND DEFINITIONS

Safety assessments will consist of monitoring and recording adverse events, including serious adverse events and adverse events of special interest, performing protocol-specified safety laboratory assessments, measuring protocol-specified vital signs, and conducting other protocol-specified tests that are deemed critical to the safety evaluation of the study.

Certain types of events require immediate reporting to the Sponsor, as outlined in Section 5.4.

### 5.2.1 Adverse Events

According to the ICH guideline for Good Clinical Practice, an adverse event is any untoward medical occurrence in a clinical investigation subject administered a pharmaceutical product, regardless of causal attribution. An adverse event can therefore be any of the following:

- Any unfavorable and unintended sign (including an abnormal laboratory finding), symptom, or disease temporally associated with the use of a medicinal product, whether or not considered related to the medicinal product

- Any new disease or exacerbation of an existing disease (a worsening in the character, frequency, or severity of a known condition), except as described in Section 5.3.5.9.
- Recurrence of an intermittent medical condition (e.g., headache) not present at baseline
- Any deterioration in a laboratory value or other clinical test (e.g., ECG, X-ray) that is associated with symptoms or leads to a change in study treatment or concomitant treatment or discontinuation from study drug
- Adverse events that are related to a protocol-mandated intervention, including those that occur prior to assignment of study treatment (e.g., screening invasive procedures such as biopsies)

### **5.2.2 Serious Adverse Events (Immediately Reportable to the Sponsor)**

A serious adverse event is any adverse event that meets any of the following criteria:

- Is fatal (i.e., the adverse event actually causes or leads to death)
- Is life threatening (i.e., the adverse event, in the view of the investigator, places the patient at immediate risk of death)
  - This does not include any adverse event that had it occurred in a more severe form or was allowed to continue might have caused death.
- Requires or prolongs inpatient hospitalization (see Section 5.3.5.10)
- Results in persistent or significant disability/incapacity (i.e., the adverse event results in substantial disruption of the patient's ability to conduct normal life functions)
- Is a congenital anomaly/birth defect in a neonate/infant born to a mother exposed to study drug
- Is a significant medical event in the investigator's judgment (e.g., may jeopardize the patient or may require medical/surgical intervention to prevent one of the outcomes listed above)

The terms "severe" and "serious" are not synonymous. Severity refers to the intensity of an adverse event (e.g., rated as mild, moderate, or severe, or according to NCI CTCAE; see Section 5.3.3); the event itself may be of relatively minor medical significance (such as severe headache without any further findings).

Severity and seriousness need to be independently assessed for each adverse event recorded on the eCRF.

Serious adverse events are required to be reported by the investigator to the Sponsor immediately (i.e., no more than 24 hours after learning of the event; see Section 5.4.2 for reporting instructions).

### **5.2.3 Adverse Events of Special Interest (Immediately Reportable to the Sponsor)**

Adverse events of special interest are required to be reported by the investigator to the Sponsor immediately (i.e., no more than 24 hours after learning of the event; see Section 5.4.2 for reporting instructions). Adverse events of special interest for this study include the following:

Adverse Events of Special Interest for GDC-0853

- Any serious infection, any infections requiring IV antimicrobials and any opportunistic infections
- Any bleeding event Grade 2 or above
- All malignancies
- A laboratory result of Grade  $\geq 3$  (i.e.,  $> 5 \times \text{ULN}$ ) AST or ALT elevation

Adverse Events of Special Interest for General Drug Development

- Cases of potential drug-induced liver injury that include an elevated ALT or AST in combination with either an elevated bilirubin or clinical jaundice, as defined by Hy's law (see Section 5.3.5.6)
- Suspected transmission of an infectious agent by the study drug, as defined below  
Any organism, virus, or infectious particle (e.g., prion protein transmitting transmissible spongiform encephalopathy), pathogenic or non-pathogenic, is considered an infectious agent. A transmission of an infectious agent may be suspected from clinical symptoms or laboratory findings that indicate an infection in a patient exposed to a medicinal product. This term applies only when a contamination of the study drug is suspected.

## **5.3 METHODS AND TIMING FOR CAPTURING AND ASSESSING SAFETY PARAMETERS**

The investigator is responsible for ensuring that all adverse events (see Section 5.2.1 for definition) are recorded on the Adverse Event eCRF and reported to the Sponsor in accordance with instructions provided in this section and in Section 5.4 – Section 5.6.

For each adverse event recorded on the Adverse Event eCRF, the investigator will make an assessment of seriousness (see Section 5.2.2 for seriousness criteria), severity (see Section 5.3.3), and causality (see Section 5.3.4).

### **5.3.1 Adverse Event Reporting Period**

Investigators will seek information on adverse events at each patient contact. All adverse events, whether reported by the patient or noted by study personnel, will be recorded in the patient's medical record and on the Adverse Event eCRF.

**After informed consent** has been obtained **but prior to initiation of study drug**, only serious adverse events caused by a protocol-mandated intervention (e.g., invasive

procedures such as biopsies, discontinuation of medications) should be reported (see Section 5.4.2 for instructions for reporting serious adverse events).

**After initiation of study drug**, all adverse events will be reported until 8 weeks after the last dose of study drug the patients receives, either in this study or in an OLE, if initiated.

Instructions for reporting adverse events that occur after the adverse event reporting period are provided in Section 5.6.

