#### **4.4 CONCOMITANT THERAPY, PROHIBITED FOOD, AND ADDITIONAL RESTRICTIONS**

Concomitant therapy includes any medication (e.g., prescription drugs, over-the-counter drugs, vaccines, herbal or homeopathic remedies, nutritional supplements) used by a patient from 7 days prior to initiation of study drug through 8 weeks after the last dose of study drug or entrance into an OLE, if initiated, whichever occurs first. All concomitant medication taken during the study must be documented on the eCRF along with indication, daily dose, and start and stop dates of administration. Adverse events related to the administration of a concomitant medication or the performance of a procedure must also be documented on the appropriate adverse event page of the eCRF.

It is recommended that patients avoid changing other *concomitant* prescription or non-prescription drugs, vitamins, and dietary supplements within 7 days or 5 half-lives, whichever is longer, prior to the first dose of study medication and throughout the study.

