### **4.6.2 Study Treatment Discontinuation**

Patients must discontinue study treatment (and will continue in the study) if they experience any of the following:

- Requirement of any prohibited medication as defined in [Section 4.4.2](#)
- Treated with accepted immunosuppressive that exceeds the maximum dose as defined by the protocol (see [Section 4.4.1](#))
- Combination immunosuppressive medications not allowed in the inclusion and exclusion criteria (see [Section 4.1](#))

- Grade >2 AST or ALT elevation: (AST or ALT >3×ULN) in combination with total bilirubin >2×ULN or clinical jaundice as defined by Hy's law
- Grade ≥3 AST or ALT elevation: (AST or ALT >5×ULN)
- Grade 4 Neutropenia: ANC <500/mm^3
- Grade 4 Lymphopenia: absolute lymphocyte count (ALC) <200/mm^3
- Grade 4 Thrombocytopenia: platelet count <25,000/mm^3
- Pregnancy
- Malignancy (with the exception of non-serious local and resectable basal or squamous cell carcinoma of the skin)
- An episode of torsade de pointes

Patients must discontinue study treatment if they receive any new or increased dose of SLE treatment that is not specifically permitted in this protocol (see Section 4.4.1) and approved by the Medical Monitor.

Investigators may discontinue study treatment for:

- Any medical condition that may jeopardize the patient's safety if he or she continues on study treatment
- The best interest of the patient
- Patient non-compliance

If study treatment is discontinued prematurely, patients will be asked to stay in the study and continue with all scheduled visits for the remainder of the 48-week treatment period.

The primary reason for study treatment discontinuation should be documented on the appropriate eCRF. Patients who discontinue study treatment prematurely will not be replaced.

In some cases, study treatment may be resumed if approved by both the investigator and the Medical Monitor.

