### 5.3.5.7 Deaths

All deaths that occur during the protocol-specified adverse event reporting period (see Section 5.3.1), regardless of relationship to study drug, must be recorded on the Adverse Event eCRF and immediately reported to the Sponsor (see Section 5.4.2). This includes death attributed to progression of lupus.

Death should be considered an outcome and not a distinct event. The event or condition that caused or contributed to the fatal outcome should be recorded as the single medical concept on the Adverse Event eCRF. Generally, only one such event should be reported. If the cause of death is unknown and cannot be ascertained at the time of reporting, "**unexplained death**" should be recorded on the Adverse Event eCRF. If the cause of death later becomes available (e.g., after autopsy), "unexplained death" should be replaced by the established cause of death. The term "sudden death" should not be used unless combined with the presumed cause of death (e.g., "sudden cardiac death").

If the death is attributed to progression of lupus, "*systemic lupus erythematosus* progression" should be recorded on the Adverse Event eCRF.

Deaths that occur after the adverse event reporting period should be reported as described in Section 5.6.

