### **5.4.2.2 Events That Occur after Study Drug Initiation**

After initiation of study drug, serious adverse events and adverse events of special interest will be reported until 8 weeks after the last dose of study drug the patients receives, either in this study or an OLE, if initiated. Investigators should record all case details that can be gathered immediately (i.e., within 24 hours after learning of the event) on the Adverse Event eCRF and submit the report via the electronic data capture (EDC) system. A report will be generated and sent to Safety Risk Management by the EDC system.

In the event that the EDC system is unavailable, the Serious Adverse Event/Adverse Event of Special Interest Reporting Form provided to investigators should be completed and submitted to the Sponsor or its designee immediately (i.e., no more than 24 hours after learning of the event), either by faxing or by scanning and emailing the form using the fax number or email address provided to investigators. Once the EDC system is available, all information will need to be entered and submitted via the EDC system.

Instructions for reporting serious adverse events that occur after the last dose of study treatment are provided in Section 5.6.

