### **5.6 ADVERSE EVENTS THAT OCCUR AFTER THE ADVERSE EVENT REPORTING PERIOD**

The Sponsor should be notified if the investigator becomes aware of any serious adverse event that occurs after the end of the adverse event reporting period (defined as 8 weeks after the last dose of study drug the patients receives, either in this study or an OLE, if initiated), if the event is believed to be related to prior study drug treatment. These events should be reported through use of the Adverse Event eCRF. However, if the EDC system is not available, the investigator should report these events directly to the Sponsor or its designee, either by faxing or by scanning and emailing the Serious Adverse Event/Adverse Event of Special Interest Reporting Form using the fax number or email address provided to investigators.

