- j After informed consent has been obtained but prior to initiation of study drug, only serious adverse events caused by a protocol-mandated intervention should be reported. After initiation of study drug, all adverse events will be reported until 8 weeks after the last dose of study drug. After this period, the Sponsor should be notified if the investigator becomes aware of any serious adverse event that is believed to be related to prior study drug treatment (see Section 5.6). The investigator should follow each adverse event until the event has resolved to baseline grade or better, the event is assessed as stable by the investigator, the patient is lost to follow-up, or the patient withdraws consent. Every effort should be made to follow all serious adverse events considered to be related to study drug or trial-related procedures until a final outcome can be reported.
- k Includes respiratory rate, pulse rate, temperature, and systolic and diastolic blood pressures while the patient is in a seated position for at least 5 minutes.
- l Include an evaluation of the head, eyes, ears, nose, and throat, and the cardiovascular, dermatological, musculoskeletal, respiratory, gastrointestinal, genitourinary, and neurological systems. Any abnormality identified at baseline should be recorded on the General Medical History and Baseline Conditions eCRF. Particular attention should be given to evaluation of potential manifestations of active SLE (see Appendix 9 BILAG 2004 Index; Appendix 10, SLEDAI-2K; Appendix 14, CLASI; and Appendix 13, 28-Joint Counts, Appendix 11, SFI) and of infections or other medical conditions, which could place the patient at increased risk.
- m Limited, efficacy assessment-directed or symptom-directed physical examinations should be performed *that also allow for completion of SLEDAI-2K and BILAG-2004 assessments*. Changes from baseline abnormalities should be recorded in patient notes. New or worsened clinically significant abnormalities should be recorded as adverse events on the Adverse Event eCRF.

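### Adverse event reporting closes 8 weeks after the last dose, although patients who stop study drug early are kept in the blinded study to Week 48

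*Combined protocol and SAP*

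**What the plan says.** **The window is counted from the last dose.** Section 5.3.1: "all adverse events will be reported until 8 weeks after the last dose of study drug the patients receives", whether that dose falls in this study or in an extension. Section 5.4.2.2 says that "serious adverse events and adverse events of special interest will be reported until 8 weeks after the last dose of study drug". Section 5.6 defines the reporting period the same way, and footnote j attaches the limit to the adverse event row of the Appendix 1 schedule.

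**After the window.** Section 5.6 asks for a serious event only if the investigator becomes aware of it and "if the event is believed to be related to prior study drug treatment". Section 5.3.5.7 requires reporting, whatever the cause, for "All deaths that occur during the protocol-specified adverse event reporting period" and sends later deaths to Section 5.6.

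**Patients off drug stay in.** Section 4.6.2: "If study treatment is discontinued prematurely, patients will be asked to stay in the study and continue with all scheduled visits", through the 48-week treatment period. Table 4 footnote a says that those who stop because of an adverse event should remain in the blinded study if feasible and cannot enter the extension.

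**Text pointing the other way.** Section 5.3.1 opens with "Investigators will seek information on adverse events at each patient contact" and no time limit. Section 5.3.2 expects adverse events to be elicited at every evaluation, and the Appendix 1 grid marks them at every clinic visit.

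**Concomitant drugs.** Section 4.4 defines concomitant therapy "through 8 weeks after the last dose of study drug or entrance into an OLE, if initiated, whichever occurs first", but its next sentence requires everything taken during the study to be documented.

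**Analysis.** Section 6.5 defines a treatment-emergent event as one that falls inside the reporting period.

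**The concern.** A patient who stops study drug early stays randomised, blinded and under observation at 4-week visits, yet the duty to report adverse events regardless of cause can lapse long before Week 48. From then on, what is reported depends on the investigator's view of causality.

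These patients are not a random subset. Section 4.6.2 stops drug for liver enzyme elevations, Grade 4 cytopenias, malignancy and the need for prohibited medication. Some may plausibly be at raised risk of later infection or malignancy, both of which matter as AESIs under Section 5.2.3. If early stopping differs between arms, the time over which unrelated-judged events are captured also differs, and an arm with more stopping would tend to show fewer of them. That weakens the between-arm safety comparison and the monitoring for imbalances described in Section 5.7.

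The conflicting text adds a second problem. A site following the opening of Section 5.3.1 would keep recording, and a site following footnote j would not.

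**Working it through.** **Check of the timeline.** Section 3.2.1 states a maximum of 61 weeks on study. Screening 35/7 = 5 weeks, plus 48, plus 8, gives 61, as stated. In Appendix 1, Day 337 is (337 − 1)/7 = Week 48 and Day 393 is (393 − 1)/7 = Week 56.

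**Inputs.** The window closes 8 weeks after the last dose (5.3.1). An off-drug patient attends visits to Week 48 (4.6.2).

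**Formula.** For a last dose at Week W the window closes at Week W + 8. In-study time to Week 48 outside it is max(0, 48 − (W + 8)) = max(0, 40 − W) weeks. As a share of the 48 weeks this is (40 − W)/48; as a share of the off-drug time it is (40 − W)/(48 − W).

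| Last dose (Week W) | Window closes | Weeks outside window | Share of 48 weeks | Share of off-drug time to Week 48 |
|---|---|---|---|---|
| 4 | 12 | 36 | 75% | 82% |
| 8 | 16 | 32 | 67% | 80% |
| 12 | 20 | 28 | 58% | 78% |
| 16 | 24 | 24 | 50% | 75% |
| 24 | 32 | 16 | 33% | 67% |
| 32 | 40 | 8 | 17% | 50% |
| 36 | 44 | 4 | 8% | 33% |
| 40 or later | 48 or later | 0 | 0% | 0% |

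More than half of the 48 weeks falls outside the window only when the last dose is before Week 16.

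**What is and is not captured after the window**

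- Need not be reported: non-serious events; AESIs that are not also related SAEs; SAEs and deaths judged unrelated.
- Still reported: SAEs, including deaths, believed related (5.6).
- Still collected: scheduled laboratory tests, vital signs and disease activity scores (Appendix 1); oral steroid use (4.3.2.4); immunosuppressant changes and escape therapy (4.3.2.3.1 and 4.3.2.3.4).
- Still followed: events that began inside the window, until resolved or stable (5.5.1).

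**Illustration only.** The documents give no rate, timing or retention for early stopping. Assume that 10%, 15% or 25% of 80 patients per arm stop (8, 12 or 20), all at Week 16, and that all stay to Week 48. Time outside the window is then 24 × 8 = 192, 24 × 12 = 288 or 24 × 20 = 480 patient-weeks per arm. Against 80 × 48 = 3,840 planned patient-weeks, that is 5.0%, 7.5% or 12.5%. If only half stay, the figures halve to 96, 144 and 240 patient-weeks (2.5%, 3.75% and 6.25%).

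**The case against.** The strongest reply is that collection does not clearly stop. The opening of Section 5.3.1, Section 5.3.2 and the visit grid can all be read as requiring recording at every visit. That is fair, and it means loss of data is not certain. But the specific rule is the 8-week limit, footnote j ties it to the grid, and no text extends it for patients off drug. What stands is a stated cut-off plus a contradiction.

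The sponsor could also say that GDC-0853 is a reversible inhibitor and that 8 weeks is the protocol's consistent safety follow-up. As a window for drug-attributable events that is defensible, and nothing in the documents shows it to be too short for that purpose. It does not answer the question of ascertainment by randomised arm.

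Three stronger readings are tempting, and the documents do not support them:

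- A reader might infer that safety follow-up of these patients ends. It does not, given the data streams that continue.
- A reader might infer that unrecorded drugs undermine the Week 48 responder analysis. Steroid, immunosuppressant and escape therapy have their own forms with no 8-week limit, and Section 4.4 also requires all medication during the study to be documented. Its end date is an internal inconsistency, not a demonstrated hole in the efficacy data.
- A reader might infer that Section 6.5 removes all late events from analysis. The restriction defines treatment-emergent events only. The separate summaries of SAEs, AESIs, deaths and malignancies state no such limit, although they can contain only what was reported.

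**Conclusion.** The concern holds in a limited form. For patients who stop study drug before Week 40 and remain in the study, the last 40 − W weeks to Week 48 lie outside the reporting window, and the events not reportable are the non-serious ones, AESIs that are not related SAEs, and SAEs and deaths judged unrelated. Later events are also excluded from the treatment-emergent summary. The passages on when adverse events are recorded contradict each other and need reconciling.

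The gap per patient follows directly from the text, assuming that the patient attends to Week 48 and does not resume drug; Section 4.6.2 allows resumption, which would move the last dose later. The total effect cannot be computed because no early-stop rate is stated, so the patient-week figures only indicate scale. Bias between arms is conditional on stopping differing by arm. Patients who leave the study altogether follow the early-termination and safety follow-up route in Section 4.6.1 and are not affected in this way. This is a worthwhile, inexpensive improvement to the safety data and does not bear on the primary efficacy result.

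**What to change.** - **Reporting period.** In Sections 5.3.1, 5.4.2.2 and 5.6 and Appendix 1 footnote j, end reporting in this study at the later of 8 weeks after the last dose in this study and the patient's last visit in this study. At minimum, apply this to SAEs, AESIs and deaths regardless of causality. Bring Section 5.3.5.7 into line, and reconcile these places with the opening of 5.3.1, 5.3.2 and the visit grid.
- **Concomitant therapy.** In Section 4.4, make the end date agree with the section's own requirement to document all medication taken during the study.
- **Analysis.** In Section 6.5, keep the on-treatment-plus-8-weeks summary as the main display. Add an in-study summary by randomised arm that includes off-drug events.

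**Cost.** Protocol wording, eCRF guidance and one extra set of safety tables. No new visits are needed. The downside is some additional off-drug events to enter, mostly unrelated and some due to later therapy; the separate display keeps them apart from the main summary.
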